    - Discontinuation: any discontinuation, resumption of long-acting injections (with CAB LA injectable or LEN LA injectable) or oral PrEP after discontinuation
    - Oral bridging between discontinuation of CAB LA injections and resumption of CAB LA injections
    - Duration of CAB LA PrEP use in months
      - first period of use
      - cumulative use throughout the study period in case of discontinuation followed by resumption of CAB LA PrEP injection(s)
    - Baseline characteristics of users discontinuing CAB LA PrEP versus users who did not discontinue
    - Proportion of CAB LA PrEP users with at least one maintenance injection who are on CAB LA PrEP at 12 months and 24 months after initiation and at the end of the study period
- 3.5- Described patterns of HIV and other STI testing/screening, diagnosis and STI treatment
- a) Assess the incidence of HIV testing and HIV diagnosis during the first period of PrEP use by PrEP modality
  - b) Estimate the incidence of testing for STI diagnosis and STI diagnosis by PrEP modality
    - in the 6 months preceding PrEP initiation
    - during the first period of PrEP use
  - c) Describe the proportion of diagnosed STI with a relevant antimicrobial prescription
- 3.6- Among CAB LA PrEP users diagnosed with HIV (during CAB LA PrEP use or after CAB LA PrEP discontinuation)
- a) Describe the timing of incident HIV diagnoses relative to timing of CAB LA PrEP usage and testing for HIV
  - b) Describe adherence to PrEP injection schedule, HIV treatment, virologic suppression, concomitant STI diagnosis, and HIV drug resistance

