have not consistently used a condom, or have been diagnosed with a sexually transmitted infection (STI) in the past six months (US CDC, 2024). PrEP is also recommended to people who inject drugs and have an injection partner with HIV, or share needles, syringes, or other equipment to inject drugs. People who have been prescribed PEP (post-exposure prophylaxis) and report continued risk behavior or have used multiple courses of PEP may as well consider taking PrEP. People may also choose to take PrEP, even if these behaviors do not apply to them.

In 2022, of approximately 1.2 million people in the US who could benefit from PrEP, it was estimated that only around 36% had received a PrEP prescription (Fanfair, 2023). The Department of Veterans Affairs (VA) is the largest HIV care provider in the US; PrEP is a covered benefit for all enrolled Veterans (Huang, 2018). An analysis of 2014-2022 data of the Veterans Health Administration (VHA) showed an increase in the number of Veterans prescribed PrEP annually, from 361 in 2014 (5.6 per 100,000 Veterans in VHA care) to 6050 in 2022 (89.4 per 100,000) (Huang, 2025). While adherence to oral PrEP was high among Veterans in the period 2012-2016 (Huang, 2018), recent adherence data, including for long-acting injectable PrEP, are lacking. To be eligible for CAB-LA PrEP in the Veterans Health Administration, individuals must be at substantial risk of HIV acquisition (sex without condoms, recent or frequent sexually transmitted infections, sexual relationship with HIV infected partner, injection drug abuse with equipment sharing), prescribed cabotegravir by a provider experienced in PrEP, and meet at least one of the following additional criteria: intolerance to TDF/FTC or TAF/FTC, renal dysfunction, challenges with adherence to daily oral PrEP, or very high risk of HIV acquisition. Patients are excluded if they have significant noncompliance with follow-up or drug interactions with CAB (VA, 2022).

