  - Proportion of CAB LA PrEP users with at least one maintenance injection who are on CAB LA PrEP at 12 months and 24 months after initiation and at the end of the study period
- 3.5- Described patterns of HIV and other STI testing/screening, diagnosis and STI treatment
- a) Assess the incidence of HIV testing and HIV diagnosis during the first period of PrEP use by PrEP modality
  - b) Estimate the frequency of testing for STI diagnosis and STI diagnosis by PrEP modality
    - in the 6 months preceding PrEP initiation
    - during the first period of PrEP use
  - c) Describe the proportion of diagnosed STI with a relevant antimicrobial prescription
- 3.6- Among CAB LA PrEP users diagnosed with HIV (during CAB LA PrEP use or after CAB LA PrEP discontinuation)
- a) Describe the timing of incident HIV diagnoses relative to timing of CAB LA PrEP usage and testing for HIV
  - b) Describe adherence to PrEP injection schedule, HIV treatment, virologic suppression, concomitant STI diagnosis, and HIV drug resistance

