## 7.2. Study Population and Setting

### 7.2.1. Inclusion criteria

- **Veterans in care without evidence of HIV infection (Obj. 1.1)- individuals will be included if they meet all of the following criteria:**

- At least one VHA health encounter in the calendar year
- $\geq 18$  years of age
- No evidence of HIV infection at the beginning of the calendar year under analysis

- **Veterans in care with a new HIV diagnosis (Obj. 1.2):**

- Incident HIV diagnosis (refer to definition in section 7.3.3)

- **Veterans in care without evidence of HIV infection who are not on PrEP but who could benefit from PrEP (Objective set 2)- individuals meeting all of the following criteria:**

- At least one VHA health encounter during the study period
- $\geq 18$  years of age
- Any of the following criteria indicating that the individual has a risk factor for HIV acquisition or a factor linked to behaviors increasing the risk of HIV acquisition and may benefit from PrEP:
  - tested for or diagnosed with a bacterial STI in the past 12 months (gonorrhea, syphilis, chlamydia),
  - tested for HIV in the past 12 months,
  - ever had alcohol use disorder,
  - ever used illicit non-injection drugs,
  - ever used injectable drugs,
  - Black women,
  - men who have sex with men,
  - individuals aged 18-24 years,
  - any history of PrEP use
- No evidence of HIV infection at the first health encounter with a criteria for PrEP

- **Veterans in care using oral PrEP only (objective set 3)**

- At least one VHA health encounter during the study period
- $\geq 18$  years of age
- Received at least one oral PrEP prescription (TDF/FTC, TAF/FTC) between January 1 2021 and 31 December 2024
- No evidence of HIV infection at the time of the first oral PrEP prescription in the study period
- Have not received a CAB LA PrEP injection between January 1, 2021, and June 30, 2025

- **Veterans in care using CAB LA for PrEP (objective set 3)**

- At least one VHA health encounter during the study period
- $\geq 18$  years of age
- Received at least one CAB LA PrEP injection between January 1, 2021 and June 30, 2025

- No evidence of HIV infection at the time of the first CAB LA PrEP injection in the study period

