#### **7.3.2. Baseline characteristics**

The following variables will be assessed for objectives 2.1 and 3.1 at index date:

- **Demographic characteristics**

- Age (years)
- Birth sex
- Race (American Indian or Alaska Native, Asian, Black or African American, Native Hawaiian or Pacific Islander, White, Not reported)
- Ethnicity (Hispanic, not Hispanic)
- Geographic Region (Northeast, Midwest, South, West, US Territories)
- Rurality (Highly rural, Rural, Urban)
- Marital/Relationship status
- Homelessness in the past 12 months

- **Clinical characteristics**

- Number of outpatient visits in the 12 months prior to index date
- Number of primary care outpatient visits in the 12 months prior to index date
- Comorbidity burden using the Charlson Comorbidity Index
- PrEP prescriber specialty
- Psychiatric diagnoses (major depression, bipolar disorder, post-traumatic stress disorder - PTSD, schizophrenia)
- Substance use (smoking, alcohol use disorder, injection and non-injection illicit drug use disorder)
- BMI

- VACS Index 2.0
- **Sexual Behavior and Health**
  - History of STI (ever)
    - Syphilis
    - Gonorrhea
    - Chlamydia
    - Chancroid
    - Lymphogranuloma venereum
    - *Mycoplasma genitalium*
    - Hepatitis B virus (HBV)
    - Hepatitis C virus (HCV)
    - Genital herpes – Herpes Simplex Virus (HSV) 1 or 2
    - Trichomoniasis infection
    - Genital Human papilloma virus (HPV) including warts
  - History of STI (past 3 months)
    - Syphilis
    - Gonorrhea
    - Chlamydia
    - Chancroid
    - Lymphogranuloma venereum
    - *Mycoplasma genitalium*
    - Hepatitis B virus (HBV)
    - Hepatitis C virus (HCV)
    - Genital herpes
    - Trichomoniasis infection
    - Genital Human papilloma virus (HPV) including warts
  - History of PrEP use

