**b) CAB LA PrEP: among complete initiators with at least one maintenance injection**

- Total number maintenance injections administered during first period of CAB LA PrEP use (overall and by person)

- Total follow-up time for complete CAB LA initiators with at least one maintenance injection (from first CAB LA PrEP injection to study end, loss to follow-up, death or HIV acquisition, whatever comes first)
- Discontinuation: number of individuals discontinuing CAB LA PrEP and number of individuals resuming LA PrEP injections (additional CAB LA or LEN LA injections after discontinuation and time between the last injection prior discontinuation and the first injection post-discontinuation) or oral PrEP
- Oral bridging between discontinuation of CAB LA injections and resumption of CAB LA injections
- Months on regimen until first censoring (first period of CAB LA PrEP use)  
Calculated as: days from first initiation injection to censoring (study end, loss to follow-up, death, HIV acquisition, discontinuation)
- Cumulative months on regimen across all CAB LA PrEP use (including additional injections after discontinuation)
  - Continuous time on CAB LA PrEP will be calculated as:
    - If no discontinuation: days from first initiation injection to censoring (study end, loss to follow-up, death, HIV acquisition)
    - If discontinuation: days from first initiation injection to discontinuation date (i.e., 127 days after last injection)
  - Among individuals with additional injections after discontinuation, the cumulative months on CAB LA regimen will be calculated across all episodes of continuous CAB LA PrEP use
  - Individuals with incomplete initiation of their first period of CAB LA PrEP use will be excluded from this analysis even if they have additional injections after incomplete initiation
- On CAB LA PrEP at timepoints of interest – among CAB LA users with no discontinuation and among CAB LA users with discontinuation
  - 12 months: injection received between  $\geq 238$  to  $\leq 365$  days after index (up to 127 days before the 12-month mark)
  - 24 months: injection received between  $\geq 603$  to  $\leq 730$  days after index (up to 127 days before the 24-month mark)
  - Study end: injection received up to 127 days before or on study end date
- ◆ **HIV testing & STI testing/screening during first period of PrEP use (Objectives 3.5)**
  - HIV testing

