    - Incidence proportion and incidence rate of HIV testing between the start of PrEP and the first discontinuation
    - Timing of HIV tests:
      - Oral PrEP: on-schedule testing defined as receiving an HIV test  $\leq 7$  days before/at start, and 3 months (76-104 days) after each test
      - CAB LA PrEP: on-schedule testing defined as receiving an HIV test

≤7 days before/at first injection, and 14 days prior each subsequent injection

- HIV diagnosis: incidence proportion and incidence rates between index date and the 1st discontinuation
- STI testing/screening
  - Assessed during the first period of PrEP use (oral or injectable)
    - Incidence proportion and incidence rate for STI testing/screening for
      - Gonorrhea
      - Chlamydia
      - Syphilis
      - Chancroid
      - Lymphogranuloma venereum
      - *Mycoplasma genitalium*
      - Hepatitis B virus (HBV)
      - Hepatitis C virus (HCV)
      - Genital Herpes (HSV-1, HSV-2)
      - Trichomoniasis
      - Genital Human papilloma virus (HPV) including warts
    - Interval between the first 2 tests for gonorrhea, chlamydia, syphilis done during the first period of PrEP use
      - Testing 3 months (76-104 days) after last test
      - Testing 6 months (168-196 days) after last test
      - Testing 12 months (351-379 days) after last test
- STI diagnoses
  - New diagnosis of STI as noted in medical record or positive test result
  - STI diagnoses for
    - Syphilis
    - Gonorrhea
    - Chlamydia
    - Chancroid
    - Lymphogranuloma venereum
    - *Mycoplasma genitalium*
    - Hepatitis B virus (HBV)
    - Hepatitis C virus (HCV)
    - Genital Herpes (HSV-1, HSV-2)
    - Trichomoniasis
    - Genital Human papilloma virus (HPV) including warts
- Relevant prescription for a selected list of STIs  
 Proportion of STI diagnosis with a prescription within 14 days following diagnosis as follows:
  - Syphilis: benzathine penicillin G, aqueous crystalline penicillin G, procaine penicillin G + probenecid, doxycycline
  - Gonorrhea: ceftriaxone, ceftriaxone + doxycycline, gentamicin + azithromycin,

- cefixime, cefotaxime
- Chlamydia: doxycycline, azithromycin, levofloxacin, amoxicillin
- Chancroid: azithromycin, ceftriaxone, ciprofloxacin, erythromycin base
- Lymphogranuloma venereum: doxycycline, azithromycin, erythromycin base
- *Mycoplasma genitalium*: doxycycline + azithromycin, doxycycline + moxifloxacin
- Trichomoniasis: metronidazole, tinidazole

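### Objective 3.5b asks for STI testing and diagnosis in the 6 months before PrEP, but section 7.3.3 does not assess that window, and the cohort rules make it neither necessarily observed nor necessarily PrEP-free

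*Protocol*

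**What the plan says.** **Objective.** The synopsis and section 6 both list two periods for Objective 3.5b: "in the 6 months preceding PrEP initiation" and the first period of PrEP use. They name the measure differently. The synopsis has "Estimate the incidence of testing for STI diagnosis and STI diagnosis by PrEP modality"; section 6 has "Estimate the frequency of testing for STI diagnosis and STI diagnosis by PrEP modality".

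**Outcome definition.** The block in section 7.3.3 is headed "HIV testing & STI testing/screening during first period of PrEP use (Objectives 3.5"). Its STI testing entry reads "Assessed during the first period of PrEP use (oral or injectable"). STI diagnoses are listed under the same heading with no window of their own. Section 7.7.1 adds univariate Poisson regression for Objective 3.5, but no pre-PrEP window and no person-time for one.

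**Baseline.** Section 7.3.2 records STI history ever and "History of STI (past 3 months"). Both are histories of infection, not of testing.

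**Entry and index.** For objective set 3, section 7.2.1 requires "At least one VHA health encounter during the study period". Table 2 sets the index at the start of the first regimen in the study period, which is the dispensing date for oral PrEP and the injection date for CAB LA. Neither cohort has a washout from earlier PrEP.

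**The concern.** Half of Objective 3.5b has no outcome definition, and the definition that exists is worded so as to leave that half out. This is a contradiction within the protocol, not a detail deferred to an analysis plan.

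An analyst who filled the gap with the cohorts as defined would meet two further problems. A Veteran whose first VHA contact is the PrEP visit has 6 prior months in which VHA records could hold no test or diagnosis. A Veteran already taking PrEP has 6 prior months that are not pre-PrEP at all. A figure labelled pre-PrEP would then mix three kinds of time (unobserved, on PrEP, and truly before PrEP) in proportions that may differ between oral and CAB LA users. Readers will naturally set it beside the during-use figure for each modality.

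**Working it through.** The protocol gives no pre-PrEP STI rate, no person-time for the window, no share of starters new to VHA and no share with prior PrEP. There is therefore no stated figure to reproduce. The check compares the sections, then illustrates direction with assumed inputs.

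**Step 1: is the window defined anywhere?**

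| Place | STI tests | STI diagnoses |
|---|---|---|
| Objective 3.5b (synopsis, section 6) | 6 months before, and first use | 6 months before, and first use |
| 7.3.3, Objective 3.5 | first use only | no own window; under the first-use heading |
| 7.3.2 baseline | none | history, ever and 3 months |
| 7.7.1 | no window | no window |

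The 6-month window appears only in the objective.

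**Step 2: is the window observed?** The single required encounter may fall at any time in 2021-2025 and can be the PrEP visit itself. Outpatient visits in the prior 12 months are a descriptive variable in 7.3.2, not an entry condition.

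**Step 3: is the window PrEP-free?**
- *CAB LA.* The index is the first injection. Oral lead-in, which Objective 3.2 counts as an initiation route, precedes it. Earlier oral PrEP does not exclude. The protocol anticipates such use: section 5 lists "challenges with adherence to daily oral PrEP" among the additional VHA criteria for CAB LA, and the Objective 3.6 timeline includes earlier oral prescriptions. Table 2's wording could put a switcher's index at an oral dispensing, but its parenthesis and section 7.2.1 point to the injection.
- *Oral.* Entry is the first prescription in the study period. A Veteran continuing oral PrEP on 1 January 2021 enters at a renewal, and the prior 6 months are on PrEP.

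**Step 4: direction, with assumed inputs.**

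(a) *Unobserved time.* A share u is out of VHA care for a fraction f of the window, and the full 0.5 year is counted.
Observed/true = 1 − u·f.
u = 5%, f = 0.5: 1 − 0.025 = 0.975. u = 30%, f = 1: 0.70.

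(b) *Prior oral PrEP.* A share s of CAB LA starters is on oral PrEP throughout the window, with rate ratio k against PrEP-free time. Section 5 describes 3-monthly visits on oral PrEP and calls STI screening an important part of follow-up, so k above 1 is plausible.
Mixed/PrEP-free = 1 − s + s·k.
k = 1, any s: 1.0. s = 80%, k = 3: 0.2 + 2.4 = 2.6.

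(c) *Both, with 10% unobserved.* 0.9 × 1.0 = 0.90, up to 0.9 × 2.6 = 2.34.

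(d) *Initiation work-up.* If a share q has one test at work-up that counts inside the window, the added rate is q/0.5 per person-year. q = 25%: 50 per 100 person-years. q = 100%: 200 per 100 person-years.

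Component (a) pushes down; (b) and (d) push up. The combined range in (c) spans 1.

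**The case against.** The other side has several fair points.

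- **Person-time rules are commonly left to the analysis plan.** The downward bias in (a) arises only if the full 6 months is counted; counting observed time removes it. Section 6 asks for a frequency, which need not use person-time at all. This stands, and it is why no bias can be asserted from this protocol alone.
- **The study is descriptive.** A reader might infer that the pre-PrEP rate is biased low and that a during/before ratio is inflated accordingly. The documents do not support this. No such ratio or contrast is planned, no denominator is stated, and prior-user monitoring acts in the opposite direction.
- **Prior oral PrEP among CAB LA users is not quantified.** Section 5 requires at least one of several additional criteria. Renal dysfunction and very high risk imply no oral PrEP, and none of the criteria carries a 6-month time frame. Prior use is expected in some users; that most had it cannot be read from the text.
- **Cohort wording speaks of initiators,** and section 7.9 dates oral initiation from the first dispensing. But Table 2 and section 7.2.1 tie entry to the first regimen or prescription within the study period.
- **Partial mitigation exists.** Prior-year visits and history of PrEP use will be described at baseline. That shows the mix but does not separate it in the STI figures.
- **The 3-month baseline look-back is not an error.** It serves Objectives 2.1 and 3.1 and contradicts nothing; it simply cannot stand in for the 6-month window.

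None of this removes the conflict between Objective 3.5b and section 7.3.3, or the absence of entry rules that make the window observed and PrEP-free.

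**Conclusion.** The point holds in a limited form. Objective 3.5b and section 7.3.3 contradict each other on the assessment period. The entry and index rules do not ensure that the 6 months before index are observed in VHA or free of PrEP, in either modality. A pre-PrEP figure computed under these rules could not be interpreted as such.

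Net direction and size cannot be derived from the documents. Under the assumed inputs above, unobserved time multiplies the rate by 0.70 to 0.975, prior oral PrEP multiplies the CAB LA rate by 1.0 to 2.6, and the latter with 10% unobserved gives 0.90 to 2.34. These figures only show that the components oppose each other; they are not estimates. The matter should be corrected, but it touches one descriptive sub-objective and no other analysis.

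**What to change.** 1. In section 7.3.3, add the 6 months before index as a second assessment window for STI tests and STI diagnoses, and state whether tests on the index date count as pre-PrEP.
2. Restrict the pre-PrEP estimates to Veterans with evidence of VHA care before the window opens, within a bounded look-back (for example, an encounter 6 to 18 months before index), or count only observed time. Without an outer bound, an encounter many years earlier would qualify and show nothing about care in the window.
3. In both modalities, report the pre-period separately for Veterans with and without PrEP dispensed in it, counting oral lead-in as PrEP for CAB LA. Splitting CAB LA alone would leave continuing users mixed into the oral group.
4. Reconcile incidence in the synopsis with frequency in section 6, and give the denominator that follows.

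The cost is protocol wording, a filter on encounter dates and a split on dispensing records. Section 7.4 says the CDW holds encounters and medications and that the national sample covers patients in VA care since 2000, so the look-back for early-2021 starters should be available. Veterans new to VHA drop out of this sub-analysis under the restriction and stay in all others. The split makes the CAB LA strata smaller than the 748 users in the feasibility count, so their intervals will be wider.

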**Table 3:** Timing of CAB LA PrEP maintenance injections, among complete initiators with  $\geq$  maintenance injection

Dosing pattern	Timing of maintenance injections (following previous injection)
On-time	53-67 days
Late	68-127 days
Short delay not requiring reinitiation	68-97 days
Long delay requiring reinitiation	98-127 days
Discontinuation	>127 days without injection

◆ **Patterns of PrEP use (Objective 3.4)**

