**a) Oral PrEP**

- Discontinuation: any discontinuation, resumption of oral PrEP after discontinuation  
Two durations will be used to identify discontinuation of oral PrEP:
  - o Oral PrEP prescription not refilled within 30 days of the previous dispensing
  - o Oral PrEP prescription not refilled within 90 days of the previous dispensing
- Duration of oral PrEP use for the first period of use

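### Objective 3.5 gives incidence proportions of HIV testing, HIV diagnosis and STI testing by PrEP modality over first periods of use that have no common time horizon

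*Protocol*

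**What the plan says.** Section 6 (Objective 3.5a) sets the task: "Assess the incidence of HIV testing and HIV diagnosis during the first period of PrEP use by PrEP modality". Section 7.3.3 then fixes measure and window:

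- HIV testing: "Incidence proportion and incidence rate of HIV testing between the start of PrEP and the first discontinuation".
- HIV diagnosis: "HIV diagnosis: incidence proportion and incidence rates between index date" and the first discontinuation.
- STI testing, over the first period of oral or injectable use: "Incidence proportion and incidence rate for STI testing/screening for" eleven listed infections.

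For STI diagnosis, section 7.3.3 names no measure. Objective 3.5b speaks of incidence in the Synopsis and of frequency in section 6.

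The end of the first period depends on modality. For oral PrEP there are two alternative rules, the shorter being "Oral PrEP prescription not refilled within 30 days of the previous dispensing" and the longer using 90 days. For CAB LA, Table 3 defines discontinuation as ">127 days without injection", and section 7.3.3 dates it 127 days after the last injection. Both CAB LA statements are made for complete initiators with at least one maintenance injection.

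Section 7.7.1.1 names one estimation method for Objective 3.5: incidence rates with confidence intervals from univariate Poisson regression. It gives none for the proportions.

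**The concern.** An incidence proportion is the share of people who have the event within a stated time at risk. If that time varies between people, and is closed by a different rule in each group, the proportion mixes how often the event occurs with how long people are watched. Two groups with the same rate will then generally show different proportions.

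HIV testing shows this plainly. Section 7.3.3 puts an on-schedule oral follow-up test at 76 to 104 days after the previous one. Under the 30-day rule, a person with a single oral fill leaves the window before that test can fall due. A CAB LA period closed by the 127-day rule lasts far longer.

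At stake is how the tables by modality are read. Section 11 names healthcare providers, decision-makers and regulatory and health authorities as the audience. They could take a difference in length of use, or in the discontinuation rule, for a difference in testing practice or HIV occurrence. The protocol uses fixed horizons for comparable measures: 12 months for adherence under Objective 3.3 and 12 months for Objective 2.2.

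**Working it through.** **The plan's own figure.** The protocol gives no figure on this point. Its one worked precision example (section 7.5) reproduces, 0.8 ± 1.96·√(0.8·0.2/748) = 0.771 to 0.829, but is not an input here.

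**Inputs from the protocol**

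- Oral period closed by 30 or 90 days without refill (section 7.3.3, Objective 3.4).
- CAB LA period closed 127 days after the last injection (section 7.3.3).
- Oral entry closes 31 December 2024 and CAB LA entry 30 June 2025 (section 7.2.1). Study end is 31 December 2025 (section 7.1). Minimum potential follow-up is thus 365 days for oral and 184 days for CAB LA. CAB LA was approved only in December 2021 (section 5), so its maximum is about four years against five for oral.

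**Inputs assumed**, because the protocol gives none: event rates r of 0.005, 0.4 and 4 per person-year, constant and equal in both groups, and mean period lengths of 0.25 to 1.5 years.

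**Step 1: shortest periods under the rules.** Oral with one fill, if the period closes when the limit is reached: 30 or 90 days. CAB LA with three on-time injections: about 30 + 60 + 127 = 217 days (23 + 53 + 127 = 203 at the earliest on-time limits).

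**Step 2: proportion at equal rates over these windows.** P = 1 − exp(−r·days/365.25).

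| r per year | 30 days | 90 days | 217 days |
|---|---|---|---|
| 0.4 | 3.2% | 9.4% | 21.2% |
| 4 | 28.0% | 62.7% | 90.7% |

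These are the extremes of short use, not averages. The first two columns show that the choice of oral rule alone can move the oral figure.

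**Step 3: varying lengths.** With exponential lengths of mean m years, P = r/(r + 1/m).

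| r per year | m = 0.5 | m = 1.0 | Ratio |
|---|---|---|---|
| 0.4 | 0.4/2.4 = 16.7% | 0.4/1.4 = 28.6% | 1.7 |
| 4 | 4/6 = 66.7% | 4/5 = 80.0% | 1.2 |
| 0.005 | 0.005/2.005 = 0.25% | 0.005/1.005 = 0.50% | 2.0 |

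At r = 0.4 the gap is 11.9 points. Table 4 gives confidence interval widths of at most 7 points for CAB LA and 2 for oral, so sampling error would not hide a gap of that size.

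**Step 4: does the repair work?** With censoring at discontinuation and a common time t, Kaplan-Meier targets 1 − exp(−r·t). At r = 0.4 this is 18.1% at 6 months and 33.0% at 12 months, whatever the period lengths. If discontinuation is instead treated as a competing event (Aalen-Johansen), the target at one year is r/(r+d)·[1 − exp(−(r+d))] with d = 1/m:

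- m = 0.5: 0.1667 × (1 − exp(−2.4)) = 15.2%
- m = 1.0: 0.2857 × (1 − exp(−1.4)) = 21.5%

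So about 15% versus 22% at equal rates: the dependence on length returns.

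**The case against.** The case against has real weight.

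- A person-time rate is planned beside every one of these proportions, and it is the only measure with a stated estimation method. Duration of the first period is also reported for both modalities under Objective 3.4, so a reader can see a difference in length.
- Section 7.5 says the study is not designed for hypothesis testing. The only tests planned compare CAB LA users with each other. Reporting by modality is stratified description, and the share tested at least once during first use has some meaning of its own.

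Both points stand and limit the matter to how the proportions are defined and read. They do not supply a horizon: following the plan still gives proportions that can differ at equal rates.

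A reader might infer more, and the document does not support it:

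- **That the proportions will mainly show period length, with two- to four-fold gaps.** At 40 per 100 person-years, such gaps need mean lengths differing three-fold (0.5 versus 1.5 years: 16.7% versus 37.5%) or six-fold (0.25 versus 1.5 years: 9.1% versus 37.5%). At 4 tests per year even the six-fold contrast gives 50.0% versus 85.7%, a ratio of 1.7.
- **That STI diagnosis is equally affected.** No proportion is named for it in section 7.3.3.
- **That every discontinued CAB LA period runs 127 days past the last injection.** That rule is set for complete initiators with a maintenance injection. Incomplete initiation is defined by more than 67 days without injection, and the text does not say what closes the period for those users under Objective 3.5.

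**Conclusion.** The point holds for the incidence proportions of HIV testing, HIV diagnosis and STI testing. They have no common horizon, the closing rules and entry windows differ by modality, and so the crude proportions partly reflect length of observation. Doubling the mean length from 0.5 to 1.0 year changes the proportion 1.7-fold at 40 per 100 person-years and 1.2-fold at 4 tests per year. These sizes rest on assumed constant, equal rates and exponential lengths.

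The direction is not known in advance. The 127-day rule lengthens CAB LA periods, while later availability and later entry shorten its potential follow-up, and realised persistence is not given. The document does not support inferring that the whole description by modality is unsound: the Poisson rates do not have this defect and should carry that description.

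**What to change.** In section 7.3.3 (Objective 3.5) and section 7.7.1.1, do one of the following:

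1. Replace the crude proportions with cumulative incidence at common times after index, for example 6 and 12 months, by Kaplan-Meier with censoring at discontinuation, loss to follow-up or study end. Death may be handled as a competing event; discontinuation should not be. State the assumption that stopping is unrelated to event risk.
2. Drop the crude proportions and report rates only, with person-time by modality.

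Under either option, state which of the two oral discontinuation definitions closes the first period for Objective 3.5, and which rule applies to incomplete CAB LA initiators.

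The cost is a wording change, a standard routine and a few more table lines. Option 1 also brings the independent-censoring assumption, which may not hold if people stop PrEP because their risk has changed.
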